## 16 Trial or site discontinuation

The trial leaders (Principal Investigator in Melbourne and Geneva) reserve the right to discontinue the trial at any time for the following reasons:

- Emergence of safety of other information that could significantly affect the continuation of the trial;
- Failure to meet expected enrolment goals overall or at a particular trial site;
- Violation of GCP or the agreement of the investigator to conduct the trial appropriately.

## 17 Statistical Analysis

Baseline characteristics will be summarized using median (interquartile range) for quantitative variables and frequency and percentage for qualitative variables.

### 1. Analysis of the primary endpoint:

To study rosuvastatin effect from baseline to week 96 on mean and / or of left and right maximal IMT progression, multi-levels, repeated measures, linear mixed-effects models adjusted for demographics and/or traditional CVD risk factors and centre (Melbourne, Geneva, Lausanne, Berne, Zurich, Basel, St. Gallen, Lugano) will be used. Levels used for the data will be patient and carotid artery locations (CCA, ICA, BIF and ECA) within patients; the repeated measure will be time (baseline, week 48 and week 96).

A comparison across arms (placebo/rosuvastatin) of missing IMT measurements (0, 1, 2 or 3 missing per IMT location) will be performed using a Chi-Square Test with a threshold of 1%.

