## 7 Study objectives

### 7.1 Primary Objective

The primary objective is to determine the effect of rosuvastatin on atherosclerosis progression in individuals with HIV infection who are at moderate cardiovascular risk.

The primary outcome measure will be the difference in cIMT progression (measured as a change from baseline) between the rosuvastatin and placebo arms.

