#### Randomisation

A computerized random number generator will be used to assign treatment arms. Block Randomisation will be stratified by country.

There will be seven study visits over the 96 week duration of the study.

cIMT, cPWV and biomarkers of immune activation and inflammation will be

measured at screening visit and compared to values obtained after 48 and 96 weeks of treatment with the study medication.

cIMT and cPWV measurements will be performed in duplicate, by the same operator at the AH Heart Centre or the Swiss site, who will remain blinded to participant randomization, throughout the study.

All samples will be processed on site at the AH or the Swiss site. Standard laboratory assessments (i.e. biochemistry, full blood examination (FBE), fasting lipids, hsCRP) will be processed by AH pathology department or the Swiss sites' local laboratories. Markers of innate immunity and inflammation will be performed in the Burnet laboratories. Plasma and PBMCs will be separated from research bloods samples, frozen to -140°C and stored onsite in the Burnet laboratory for possible further analysis in the future.

*For Switzerland: Plasma samples for testing of inflammation markers will be stored on site at minus 80° and shipped to central biobank (sérothèque) HUG for analysis at the HUG cardiology laboratory.*

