### 2. Analysis of the secondary endpoints:

To study rosuvastatin effect from baseline to week 48 on mean and / or of left and right maximal IMT progression, multi-levels, repeated measures, linear mixed-effects models adjusted for demographics and/or traditional CVD risk factors and centre will be used. Levels used for the data will be patient and carotid artery locations (CCA, ICA, BIF and ECA) within patients; the repeated measure will be time (baseline and week 48).

Repeated measures linear mixed-effects models adjusted for demographics and/or traditional CVD risk factors and centre will be used to assess the association between the arms (placebo/rosuvastatin) and each of the following parameters at week 0, 12, 24, 48, 72 and 96. We will test the interaction term between the arms and time (Month 0, 6, 12 and 24) to determine whether the rate of progression of the following parameters differed between arms (rosuvastatin versus placebo): Fasting Total Cholesterol, low-density lipoprotein (LDL)-cholesterol, high-density lipoprotein (HDL)-cholesterol, triglycerides and glucose.

Biomarkers of inflammatory process (sCD14, sCD163, neopterin, S-VCAM-1, adiponectin, CCL2, inflammatory (CD16+) monocyte expression of CD38, CX3CR1 and CD11b) will be

analysed using the same kind of regression with the same adjustments as described above including (LDL)-cholesterol and (HDL)-cholesterol.

The rate of adverse effects (symptomatic and biochemical) from the safety report will be summarized using frequency and percentage.

All efficacy analyses will compare the randomised treatment groups on an intention to treat basis regardless of treatments received during the study, including all patients with data at randomisation and at least one follow-up visit. Primary endpoint analyses will use a last value-carried forward approach for any patients permanently lost to follow-up. Secondary endpoints analyses will only include available data.

Statistical analysis will be performed using STATA Release 12.0 or updated version (Stata Statistical Software: Release 12.0, Stata Corporation, and College Station, USA).

We plan to recruit 102 patients. Drop outs will not be replaced unless the number surpasses the attrition rate of 15%.

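### Read as baseline main effects, centre and risk factors adjust IMT level but not progression in the primary model; the randomisation stratum and a few covariates should be allowed to act on change

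*Combined protocol and SAP*

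**What the plan says.** Section 7.1 defines the primary outcome as "the difference in cIMT progression (measured as a change from baseline) between the rosuvastatin and placebo arms". Section 17 (analysis of the primary endpoint) uses "linear mixed-effects models adjusted for demographics and/or traditional CVD risk factors and centre". It places baseline among the outcomes: "the repeated measure will be time (baseline, week 48 and week 96". The hierarchy is also given: "Levels used for the data will be patient and carotid artery locations (CCA, ICA, BIF and ECA) within patients".

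Section 17 does not write out an arm-by-time term for IMT. It does not say whether covariates enter as main effects or with time, whether they are baseline or updated values, or whether the arms share a baseline mean. For lipids and glucose, by contrast, it names an interaction: "We will test the interaction term between the arms and time (Month 0, 6, 12 and 24".

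On missing data, Section 17 says: "Primary endpoint analyses will use a last value-carried forward approach for any patients permanently lost to follow-up". Secondary analyses use available data only.

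On randomisation, Section 8.1 says: "Block Randomisation will be stratified by country". Section 12.4 names centre as the stratification factor instead.

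**The concern.** When baseline is part of the outcome vector, progression is a within-patient contrast. A covariate that is fixed over time and entered as a main effect shifts a patient's three IMT values by the same amount, so it cancels from every difference between visits. The announced adjustment would then leave the primary comparison as it was.

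Two things are at stake. The trial stratifies its randomisation, but the stratum would enter only the level of IMT and not the contrast that is reported. If progression differs by country, that variation stays in the residual and the standard error is larger than it need be. The trial also collects age, sex, smoking and other risk factors at entry, and would gain no precision on progression from them.

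**Working it through.** **The plan's own figure.** Section 6.6 gives an effect of 0.076 mm, SD 0.09 mm, alpha 1%, power 90% and 44 per group; two-sided testing is assumed here. A noncentral t calculation gives 89.7% power at 43 per group and 90.5% at 44, so 44 reproduces. The total of 102 matches 88 × 1.15 = 101.2, rounded up. This calculation uses an unadjusted t-test and does not rely on covariates.

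**Algebra.** Write the model for patient i at visit t as

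Y(i,t) = α + γX(i) + βA(i) + τ(t) + δ(t)A(i) + patient effect + error,

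with X fixed at baseline, A the arm and δ(0) = 0. The change to week 96 is

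Y(i,96) − Y(i,0) = [τ(96) − τ(0)] + δ(96)A(i) + change in the random part.

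γX(i) has gone. With complete data and a common covariance matrix, the likelihood splits into a part for the changes, which contains δ but not γ, and a part for baseline given the changes, in which α and β are free. The second part carries no information about δ. If β is forced to zero (a common baseline mean), or if some visits are missing, the split is no longer exact.

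**Numerical check.** The arm-by-week-96 term was estimated with and without covariate main effects. REML random-intercept models were fitted to 40 simulated trials of 102 patients. Exact generalised least squares (GLS) was applied to 60 simulated trials under each of four covariance structures: compound symmetry, random slope, unstructured and four locations nested in patient. Level SDs and covariate effects are assumptions. The SD of change was at or near 0.09 mm, except in the unstructured case (about 0.145 mm).

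| Setting | Shift in estimate (mm) | Change in SE |
|---|---|---|
| Fixed covariates, free baseline, complete data | at most 2e-15 | none (ratio 1.000) |
| Same, follow-up filled by carry-forward | at most 2e-15 | below 0.003% |
| Same, about 15% dropout, no imputation, REML | mean 0.0003, max 0.0010 | up to 0.11% |
| Same, dropout or missing locations, GLS | mean 0.0001 to 0.0018, max 0.0004 to 0.012 | up to 0.24% |
| Common baseline mean, complete data | mean 0.001 to 0.006, max 0.015 | up to 1.4% |
| One time-varying covariate affected by treatment | mean about 0.015, max about 0.04 | up to about 7% |

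The 0.012 mm maximum is the worst single trial under the unstructured covariance.

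**What acting on change could gain.** If baseline covariates explain a share R² of the variance of change, the SE ratio before loss of degrees of freedom is √(1 − R²). Power, starting from the planned 90% at two-sided 1%, is Φ(3.857/√(1 − R²) − 2.576), where 3.857 = 1.282 + 2.576 up to rounding.

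- R² = 0: ratio 1.00, power 90%.
- R² = 0.05: ratio 0.975, power 91.6%.
- R² = 0.10: ratio 0.949, power 93.2%.
- R² = 0.20: ratio 0.894, power 95.9%.
- R² = 0.25: ratio 0.866 by formula. Models fitted with covariate-by-time and centre-by-time terms gave only 0.934 (complete data), 0.953 (carry-forward) and 0.948 (observed data).

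Putting the fitted ratios into the power formula gives Φ(3.857/0.953 − 2.576) = 93% and Φ(3.857/0.934 − 2.576) = 94%. The formula alone is therefore optimistic. In those fits the estimate moved by about 0.007 to 0.008 mm on average, which is a reason to fix the covariate set in advance.

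**Country alone (assumed differences).** With the planned 72/30 split, the between-country variance is (72/102)(30/102)d² = 0.208d². For a difference d in mean two-year change of 0.04 mm, the share is 0.208 × 0.0016/0.0081 = 4%. For 0.08 mm it is 16%. The matching SE ratios are √0.96 = 0.98 and √0.84 = 0.92.

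**Degrees of freedom.** Country-by-visit costs (2 − 1) × 2 = 2. Eight-centre-by-visit costs (8 − 1) × 2 = 14.

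**The case against.** The strongest reply is that the plan never says the covariates enter as main effects only. Section 7.1 speaks of change from baseline, and if change were the modelled outcome, main effects would act on progression, as the fix asks. This stands in part: the form is inferred. But Section 17 lists baseline as a repeated time point and names an interaction where it wants one, so main effects on level are the ordinary reading.

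A reader might go further and infer that the adjustment can change nothing in any of the repeated-measures models. The documents do not support that. Exact invariance needs time-fixed covariates, a free baseline arm difference and complete or filled data. Carry-forward covers permanent loss only, and Section 17 itself anticipates missing IMT by location. Smoking is asked at every visit (Section 11), and blood pressure is on the visit forms, so updated values are possible. The biomarker models add LDL-C and HDL-C, which vary over time and respond to treatment. They fall outside this point.

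A reader might also infer that the strata are ignored or that the trial's result would be invalid. Centre is in the model and determines country; what is missing is its action on change. A constant offset between ultrasound machines cancels in change. Swiss machines are accepted by the core laboratory (Section 11.3), and images go to one core facility (Section 19.3). Nothing in the documents shows that progression differs by centre.

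Finally, the R² values are assumed and the fitted gain is smaller than the formula suggests. That is correct, and the size is stated accordingly.

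**Conclusion.** The point holds for the primary IMT model under its ordinary reading: fixed baseline main effects, with the arm difference at baseline left free. The stated adjustment then leaves the arm-by-time estimate and standard error unchanged with complete or carried-forward data. With missing data the standard error stays within about 0.2%, and the estimate moves on average by less than 0.002 mm against a design effect of 0.076 mm. The randomisation stratum does not reach the progression contrast.

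The loss is one of efficiency. No bias or inflation of type I error follows, and the sample size stands. The recoverable precision is nil if R² is near 0, about 5% of the standard error at 10% before loss of degrees of freedom, and about 5 to 7% in fitted models with centre-by-time terms at 25%. The change is worth making because it is cheap and brings the stratum into the analysis of progression, but it is not essential to a valid result.

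**What to change.** State the form of the primary model in Section 17: the arm-by-visit term, how baseline is handled, and that covariates are values at entry. Then add country-by-visit, and visit interactions for a short prespecified set such as age, sex and smoking at entry. Regressing change in IMT on the same terms is equivalent. Replace the open choice of demographics and/or risk factors with that fixed list.

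Reconcile Sections 8.1 and 12.4 on whether country or centre is the stratum. Country-by-visit is preferable in either case: with 30 Swiss patients planned across up to seven sites, 14 df for centre-by-visit buys little.

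The cost is a line of SAP text and a few degrees of freedom (2 for country, plus 2 for each single-parameter covariate). If R² turns out near zero, those degrees of freedom are spent for no gain.

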k Carotid intima media thickness (cIMT) will be performed on the left and right common carotid arteries, 12 consecutive measurements will be made 1-3cm proximal to the carotid bulb in areas identified as being without plaque.

l Carotid-femoral Pulse Wave Velocity (cPWV) will be determined by using simultaneous applanation tonometry of the carotid and femoral arteries. Only for Australian site.

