## **11.3 Carotid IMT**

The bilateral carotid artery will be assessed for cIMT by B Mode ultrasound using a Philips iE33 with 11 MHz linear transducer (Melbourne). The Swiss sites will be using the ultrasound machine tested and accepted by the core lab in Montréal following the Standard Operating Procedures for cIMT. The cIMT measurement is a painless and harmless non-invasive ultrasound procedure performed on patients’ left and right common carotid arteries. The procedure takes 20 minutes to perform. The cIMT defined as the distance between lumen-intima interface and media-adventia interface is measured from the 2D high resolution digital images obtained using an automated border-detection algorithm. cIMT will be

determined on areas identified as without plaque by 12 consecutive measurements made 1-3 cm proximal to the carotid bulb, but the presence of plaques will be noted. All measurements will be performed in duplicate, by the same operator at the AH Heart Centre or the Swiss site, who will remain blinded to participant randomization, throughout the study.

Investigators and patients will not receive results from cIMT (or cPWV – see below) until the end of the study, unless a significant carotid plaque warranting further investigation and management is identified. Patients who are identified as having a significant plaque will be withdrawn from the study and referred to a cardiologist at the AH or the Swiss site for further assessment and management as necessary.

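### Section 17 models IMT at four carotid locations while the imaging text describes only the common carotid, and the primary IMT variable is not fixed

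*Combined protocol and SAP*

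**What the plan says.** **Model.** Section 17, item 1, specifies a multilevel repeated-measures mixed model for the primary endpoint, from baseline to week 96: "Levels used for the data will be patient and carotid artery locations (CCA, ICA, BIF and ECA) within patients". Item 2 uses the same structure for the week-48 model: "carotid artery locations (CCA, ICA, BIF and ECA) within patients; the repeated measure will be time (baseline and week 48". Item 1 also compares the arms on "missing IMT measurements (0, 1, 2 or 3 missing per IMT location", so the location level carries through to the missing-data check.

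**Imaging.** Flow-chart footnote k says that cIMT "will be performed on the left and right common carotid arteries, 12 consecutive measurements will be made 1-3cm proximal to the carotid bulb". Section 11.3 places the procedure on the "left and right common carotid arteries. The procedure takes 20 minutes to perform", and says that cIMT is "determined on areas identified as without plaque by 12 consecutive measurements made 1-3 cm proximal to the carotid bulb". It requires all measurements in duplicate. It does not say how the 12 measurements, the duplicates and the two sides are combined.

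**Variable.** Section 17, item 1, analyses "mean and / or of left and right maximal IMT progression". Section 7.1 defines the primary outcome as change from baseline in cIMT, without segment, summary or time point.

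**Planning.** Section 6.6 uses an effect of 0.076 mm, an SD of 0.09 mm over 2 years, a t-test at 1% and 90% power, and arrives at 44 per group. It does not say which segment or summary the SD describes.

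**Interim.** Section 15 gives the DSMB an unblinded week-48 review of cIMT, which it calls the primary endpoint measure.

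**The concern.** The primary model needs data from the internal carotid, the bifurcation and the external carotid, yet no section describes measuring IMT there. An analyst working from the imaging described could not fit the model as written. Averaged over four locations, the treatment effect is also a different quantity from the effect in the common carotid.

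Separately, the text does not identify one primary variable. If mean and maximal IMT can both be analysed, there may be two primary results, with no rule for which one counts and no error control. The interim adds a deadline: Section 15 allows an efficacy stop only for a strong statistical and clinical difference in cIMT, and that judgement needs a defined cIMT variable.

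**Working it through.** **1. Segments side by side**

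| Location in the Section 17 models | IMT measurement described in footnote k or Section 11.3 |
|---|---|
| CCA | Yes, left and right |
| ICA | None |
| BIF | None |
| ECA | None |

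Three of the four levels have no stated source. The missing-scan count of 0 to 3 fits the three imaging time points (screening, week 48, week 96). It shows that counting is by location but does not show which locations are scanned.

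**2. Readings of the primary variable**

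The phrase allows four readings:

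- (a) mean IMT;
- (b) maximal IMT;
- (c) both;
- (d) the mean of the left and right maxima, which is a single variable.

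Sections 7.1 and 11.3 do not choose between them. Section 6.6 cites a mean common-carotid progression rate from the reference study. There, mean can simply be the average across participants, as it is for the pilot figure in the same section. It supports the segment but does not settle mean against maximal thickness.

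**3. The plan's own figure**

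Inputs from Section 6.6: δ = 0.076 mm, σ = 0.09 mm, α = 1%, power 90%.

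Two-sample t-test: noncentrality = δ / (σ√(2/n)), with 2n − 2 degrees of freedom.

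- At n = 44: 0.076 / (0.09 × √(2/44)) = 3.96 on 86 degrees of freedom. Two-sided 1% gives power 90.5%.
- At n = 43: power is 89.7%, so 44 is the smallest n that reaches 90%.
- One-sided 1% would need only 38 per group, so the stated 44 implies a two-sided test.

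The 44 per group reproduces.

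**4. Illustration under reading (c)**

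Assume that two measures are each tested at two-sided 1% and that either may be claimed. With no treatment effect, P(at least one |Z| > 2.576) from a bivariate normal is:

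| Assumed correlation | False-positive rate |
|---|---|
| 0.5 | 1.90% |
| 0.7 | 1.77% |
| 0.8 | 1.66% |
| 0.9 | 1.49% |

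Independence would give 1 − 0.99² = 1.99%. Splitting the alpha to 0.5% each, at the Section 6.6 inputs, needs 49 per group; 44 per group gives 85.6% power.

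The documents give no correlation. Section 17 gives no alpha for the primary model, so the 1% used here is the planning value.

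**The case against.** **Other segments may well be imaged.** Section 11.3 opens with bilateral assessment of the carotid artery, has plaques noted, and refers to standard operating procedures for cIMT. Section 19.3 sends the images to a core facility. This objection stands as a limit on the claim. A reader might infer that the ICA, BIF and ECA data do not exist or that the primary analysis is impossible, and the documents cannot show that. If those segments are acquired, however, footnote k and Section 11.3 are incomplete and still need correcting.

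**The phrase may mean one variable.** Under reading (d) there is no multiplicity. That is fair, and it is why the error rates above are only an illustration. The text still does not say which reading applies.

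**Blinding protects the choice.** A reader might infer that the variable could be picked after seeing unblinded results. The documents do not support that: Section 15 makes the DSMB independent and Section 10.11 keeps trial personnel blinded. Blinding does not, however, tell the analyst which result is primary.

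**The inflation is small.** It is 0.5 to 0.9 percentage points under the assumptions shown. The case for correction rests on the undefined endpoint and not on that figure.

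**Conclusion.** The concern holds in two parts. First, Section 17 contradicts the imaging text: three of the four location levels in the primary and week-48 models have no stated data source. This can be read directly from the documents and needs no assumption. Second, the primary IMT variable is open to at least four readings, with no rule for choosing one or for controlling error if more than one is tested. If two were tested, the false-positive rate would be about 1.5% to 1.9% instead of 1%; this rests on assumed correlations, on both tests using 1%, and on either being allowed to count.

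Two further inferences go too far. Section 6.6 does not establish mean thickness as the intended summary. Nor do the documents show that the trial is underpowered: 44 per group is right for the stated inputs, and it is simply unknown whether the 0.09 mm SD describes the variable to be analysed. The text should be corrected before the week-48 interim.

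**What to change.** Before the week-48 interim:

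1. Make footnote k, Section 11.3 and Section 17 items 1 and 2 agree on the segments acquired and analysed.
   - If only the common carotid is imaged, replace the four-location level with side within patient, or use a left-right average, and tabulate missing scans by side and visit.
   - If other segments are acquired, describe them in footnote k and Section 11.3 and state whether they enter the primary model.
2. Name one primary IMT variable: the segment, mean or maximum, and how the sides and the duplicate sets of 12 measurements are combined. The common carotid matches the imaging text and the reference study cited in Section 6.6. Mean or maximum is the sponsor's choice.
3. Name one contrast, change from baseline (the screening scan) to week 96. Make any other summary secondary, and use the same variable at the interim.
4. State in Section 6.6 which segment and summary the 0.09 mm SD describes.

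**Cost.** Wording in Section 17 and one sentence in Section 6.6, plus footnote k and Section 11.3 if other segments are acquired. No added imaging is needed. If only the common carotid is imaged, the structure of the primary model changes. The 44 per group (two-sided 1%, 90.5% power) stands if the SD belongs to the chosen variable; otherwise the power must be restated.

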## 6.3 Statin therapy

Statins are HMG-CoA reductase inhibitors that lower total cholesterol, improve endothelial function, and halt progression of atherosclerosis. Randomized trials of rosuvastatin in the general population have shown a reduction in major CVD events and in the inflammatory biomarker high sensitivity C-reactive protein (hsCRP) in healthy adults with normal LDL levels (the JUPITER trial). High levels of baseline hsCRP were an independent predictor of CVD in this cohort. The absolute CVD event reduction with rosuvastatin was greatest in those with highest baseline hsCRP levels and in those who achieve low hsCRP levels regardless of LDL level achieved. The cIMT effect size seen with statin therapy correlates with reduction in LDL and baseline cIMT. As previously shown HIV positive people have, on average, greater cIMT and faster cIMT progression rates, thus it is likely that the magnitude of effect seen with statin therapy may be greater.

Furthermore, statins are immune modulators, and inhibit inflammation in part by reducing chemokine and pro-inflammatory cytokine synthesis by monocytes, inhibiting monocyte adhesion to the blood vessel wall as well as improving the function of other cells involved in atherogenesis (smooth muscle cells, platelets, endothelial cells). Rosuvastatin is predicted to alter the plasma levels of inflammatory markers and monocyte phenotype by week 12. Atorvastatin decreased CRP, IL-6 and CCL2 levels in 4 -6 weeks in HIV negative participants. Rosuvastatin has been shown to induce a 16% reduction in hsCRP in stable ART-treated HIV positive participants over 45 days. High dose atorvastatin over 8 weeks in ART naive HIV positive participants resulted in significant decreases in immune activation (CD4+ HLA-DR+, CD8+ HLA-DR+ and CD8+ CD38+ T cells). These effects may provide

additional benefit in HIV positive participants given high baseline levels of immune activation and inflammation and the association between these markers and CVD outcomes.

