#### 6.6 Sample size

The METEOR study of rosuvastatin in HIV negative participants with low to intermediate CVD risk found a mean Common Carotid Artery cIMT progression rate of 0.0088 mm/2 years in the placebo arm and 0.0004mm/2 years in the rosuvastatin arm^22, giving an effect size of 0.0084 mm/2 years (95% relative reduction) with a standard deviation (SD) of 0.033 mm/year. A pilot study in HIV positive patients at the AH (n=10) found that in participants treated with non-nucleoside reverse transcriptase inhibitors (the most common cART regimen), the mean cIMT progression rate was 0.04 mm/year with a SD of 0.0782 mm (personal communication [name], Baker IDI), similar to estimated values proposed for cIMT progression in HIV positive participants at low to intermediate CVD risk (mean 0.045 mm/year, SD 0.08 mm; 62).

Conservatively assuming a cIMT progression rate of 0.080 mm with a SD of 0.09 mm over 2 years and near stabilisation of cIMT (95% relative reduction) with rosuvastatin, we can assume an effect size of 0.076 mm with a SD of 0.09 mm. Sample size was calculated using an independent groups t-test with an alpha threshold of 1% and a power of 90%. Based on these hypotheses, with 44 participants in each group this study will be able to detect an effect

size of 0.076 mm with a SD of 0.09 mm over 2 years between the 2 groups. With an estimated 15% total drop-out rate over 96 weeks, we estimate that a total study population of 102 will be required.

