#### **12.4 Randomisation**

Patients will be block randomised in a 1:1 ratio to receive rosuvastatin or placebo. Randomisation will be stratified by centre.

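### The primary model does not say how baseline cIMT is used; a common baseline mean or a baseline covariate would add precision at no cost

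*Combined protocol and SAP*

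**What the plan says.** Section 7.1 defines the primary outcome as "the difference in cIMT progression (measured as a change from baseline) between the rosuvastatin and placebo arms". Section 17 (analysis of the primary endpoint) analyses cIMT with a multilevel repeated-measures linear mixed model in which "the repeated measure will be time (baseline, week 48 and week 96"). The adjustment list is demographics and/or traditional cardiovascular risk factors, and centre. Baseline cIMT is not on it.

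Three things are left unstated for cIMT: whether the two arms share one baseline mean, which covariance structure is used, and which model term is the primary estimate. The only contrast spelled out in section 17 is for fasting lipids and glucose, under the secondary endpoints. It is an arm-by-time interaction whose time points include month 0.

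Section 6.6 sizes the trial on unadjusted two-year change. It states "Sample size was calculated using an independent groups t-test with an alpha threshold of 1% and a power of 90" per cent, and "we can assume an effect size of 0.076 mm with a SD of 0.09 mm".

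**The concern.** Placing baseline in the outcome vector is not in itself an adjustment for baseline. The effect depends on a constraint that the plan does not mention.

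- If each arm has its own baseline mean, the week-96 arm-by-time term in complete data is the difference in raw change scores. The baseline difference is subtracted in full.
- If the arms share one baseline mean, which randomisation justifies because baseline is measured before treatment, the same data give the precision of an analysis of covariance. The baseline difference is then subtracted only in proportion to the correlation.

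Section 7.1, and the month-0 interaction used for lipids and glucose, both point to the first model. Precision would then be lost on the primary endpoint although baseline cIMT is already collected. Because no contrast is named, even a main effect of arm over all three visits could be reported, and that would average in a visit before any treatment was given.

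**Working it through.** **Inputs.** From section 6.6: difference 0.076 mm, SD of two-year change 0.09 mm, alpha 1%, power 90%, 44 evaluable per arm. Section 12.4 gives 1:1 allocation. The baseline to week-96 correlation ρ is not in the documents, so I show a range. I assume equal variance σ² at each visit.

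**The plan's own figure.** The normal approximation, two-sided, gives 2 × (2.576 + 1.282)² × (0.09/0.076)² = 41.7, so 42 per arm. The exact noncentral t gives 44 per arm with power 90.5%. A one-sided t-test would need only 38, so the plan's 44 is two-sided and reproduces.

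**Formulas.** Let D0 and D96 be the between-arm differences in mean cIMT at baseline and week 96, with n per arm.

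- Arms free at baseline: the estimate is D96 − D0, with variance (2/n) × 2σ²(1 − ρ).
- Common baseline mean, or baseline as covariate: the estimate is D96 − ρ × D0, with variance (2/n) × σ²(1 − ρ²).
- Ratio of the second to the first: (1 + ρ)/2. The share forgone is (1 − ρ)/2.

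With the SD of change fixed at 0.09 mm, the unadjusted standard error is 0.09 × √(2/44) = 0.0192 mm. The adjusted SD is 0.09 × √((1 + ρ)/2).

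| Assumed ρ | Variance reduction | Adjusted SD (mm) | SE at 44 per arm (mm) | Per arm for 90% power | Power at 44 per arm |
|---|---|---|---|---|---|
| none used | 0 | 0.0900 | 0.0192 | 44 | 90.5% |
| 0.5 | 25% | 0.0779 | 0.0166 | 34 | 97.2% |
| 0.7 | 15% | 0.0830 | 0.0177 | 38 | 94.9% |
| 0.9 | 5% | 0.0877 | 0.0187 | 42 | 92.1% |
| 0.95 | 2.5% | 0.0889 | 0.0189 | 43 | 91.3% |

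**Check on the three-visit model.** Generalised least squares with baseline, week 48 and week 96 as outcomes, complete data and a common correlation gave the same answers. With the arms free at baseline, the week-96 contrast had SE 0.0192 mm at every ρ. With equal baseline means, the SEs matched the table. So the outcome vector in section 17 is compatible with either result, and the constraint decides.

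**Slightly smaller n.** With 15% loss from 102, 86.7 remain, or about 43 per arm. Power there moves from 89.7% to 96.8%, 94.4%, 91.3% and 90.5% at the four correlations.

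**Locating ρ.** Since SD of change² = 2σ²(1 − ρ), ρ = 1 − 0.09²/(2σ²). The four correlations correspond to a cross-sectional SD of 0.090, 0.116, 0.201 and 0.285 mm. The documents give no such SD, but the pooled baseline data would, without unblinding.

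**Limits.** This is a two-arm approximation at one time point. It ignores the carotid-location level, the other covariates and the last-value-carried-forward rule in section 17.

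**The case against.** The sponsor can fairly say four things.

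- **The quoted sentence does not commit the plan to a change-score analysis.** This stands. A model with a common baseline mean also needs baseline as its first outcome time. The change-score result follows from the natural reading, not from the text alone.
- **A change-score analysis would be legitimate.** This stands too. It matches the outcome in section 7.1 and the t-test in section 6.6. A reader might infer bias from a chance baseline imbalance. Given a particular imbalance, the estimate does shift by (1 − ρ) times its size, but over randomisations that shift averages to zero.
- **Power is already met.** Correct on the plan's inputs: 44 per arm gives 90.5% without adjustment. A reader might infer that the trial is underpowered because baseline is not used, but the sample size was derived from unadjusted change. Whether 0.09 mm is the right SD is a separate question.
- **The gain may be small.** Section 11.3 specifies 12 consecutive measurements, duplicate readings by the same operator and automated border detection, all of which should raise ρ. At 0.95 the variance gain is only 2.5%.

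A reader might also cite section 6.3, "The cIMT effect size seen with statin therapy correlates with reduction in LDL and baseline cIMT", as evidence that baseline adjustment is needed. It does not show that. It describes a treatment effect that varies with baseline, which neither a baseline main effect nor a common baseline mean would model, and it says nothing about the baseline to week-96 correlation.

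What remains is that the plan leaves the choice open, and one option is at least as precise and uses data already in hand. The listed demographic and risk-factor covariates, entered as main effects only, do not recover this gain.

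**Conclusion.** The point holds as a free improvement and a needed clarification. On its natural reading, the primary analysis forgoes (1 − ρ)/2 of the variance of the week-96 estimate. That is material if ρ is 0.5 to 0.7 (25% to 15%) and slight if it is 0.9 to 0.95 (5% to 2.5%). The result assumes complete data, equal variances, an SD of change of 0.09 mm and an undocumented ρ. It does not show bias, an error in the sample size, or power below target.

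**What to change.** Add to section 17, for the primary endpoint, that the primary estimate is the between-arm contrast at week 96 from the arm-by-time terms, and choose one of two forms:

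- keep baseline, week 48 and week 96 as outcomes, constrain the arms to a common baseline mean, and include arm-by-time terms at weeks 48 and 96 only; or
- use weeks 48 and 96 as outcomes, with baseline cIMT as a covariate.

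Baseline should be defined at the same level as the outcome (the same carotid location if locations are modelled). The week-48 cIMT analysis should follow the same form.

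The cost is a sentence or two in section 17. cIMT is already measured at screening (sections 5 and 12.1), so no patients, visits or data are added. The wording should be settled before the unblinded interim review of cIMT described in section 15.
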